### 7.1.2 Timing of Dose Administration

Trial treatment should be administered on Day 1 of each cycle after all procedures/assessments have been completed as detailed on the Trial Flow Chart (Section 9.0). Trial treatment may be administered up to 3 days before or after the scheduled Day 1 of each cycle due to administrative or other reasons.

All trial treatments will typically be administered on an outpatient basis.

Pembrolizumab up to 200 mg will be administered as a 30 minute IV infusion every 3 weeks. Sites should make every effort to target infusion timing to be as close to 30 minutes as possible. However, given the variability of infusion pumps from site to site, a window of -5 minutes and +10 minutes is permitted (i.e., infusion time is 30 minutes: -5 min/+10 min). Pembrolizumab will be administered after the operative endoscopy. If the patient is found to have progressive disease by endoscopic evaluation, the patient will continue to receive pembrolizumab until the next in-office clinical examination in 3 weeks which confirms progressive disease of the target lesion.

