Duration of Participation	Each subject will participate in the trial from the time the subject signs the Informed Consent Form (ICF) through the final protocol-specified contact. After a screening phase of 28 days, eligible subjects will register then to receive treatment on Day 1 of each 3-week dosing cycle. Treatment with pembrolizumab will continue until documented confirmed disease progression, unacceptable adverse event(s), intercurrent illness that prevents further administration of treatment, investigator's decision to withdraw the subject, subject withdraws consent, pregnancy of the subject, noncompliance with trial treatment or procedure requirements, completion of 24 months of treatment with pembrolizumab, or administrative reasons. Subjects who attain a complete response may consider stopping trial treatment if they meet criteria for holding therapy. These subjects will be eligible for re-treatment after experiencing disease progression at the discretion of the investigator if they meet the criteria for re-treatment and the trial is ongoing. After the end of treatment, each subject will be followed for 30 days for adverse event monitoring (serious adverse events will be collected for 90 days after the end of treatment). Subjects who discontinue protocol treatment for reasons other than disease progression will have post-treatment follow-up for disease status until first disease progression, initiating a non-study cancer treatment, withdrawing consent, becoming lost to follow-up, death, or 36 months from study registration whichever occurs first. Following first disease progression, subjects will be followed by telephone for overall survival until death, withdrawal of consent, or 36 months from study registration whichever occurs first.

---

CONFIDENTIAL

*This document is confidential. Do not disclose or use unless authorized.*

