Adverse events will be monitored throughout the trial and graded in severity according to the guidelines outlined in the NCI Common Terminology Criteria for Adverse Events (CTCAE) version 4.0. Treatment with pembrolizumab will continue until documented disease progression, unacceptable adverse event(s), intercurrent illness that prevents further administration of treatment, investigator's decision to withdraw the subject, subject withdraws consent, pregnancy of the subject, noncompliance with trial treatment or procedure requirements, completion of 24 months of treatment with pembrolizumab, or administrative reasons. Subjects who attain an investigator-determined confirmed complete response (CR) may consider stopping trial treatment after receiving at least 24 weeks of treatment. Subjects who discontinue after at least 24 months of therapy for reasons other than disease progression or intolerance or who discontinue after attaining a CR may be eligible for up to one year of re-treatment after they have experienced clinical and/or radiographic disease progression. The decision to retreat will be at the discretion of the investigator if no additional systemic immunotherapeutic treatment was administered since the last dose of pembrolizumab, the subject still meets the safety parameters listed in the Inclusion/Exclusion criteria and the trial remains open.

---

CONFIDENTIAL

*This document is confidential. Do not disclose or use unless authorized.*

After the end of treatment, each subject will be followed for 30 days for adverse event monitoring (serious adverse events will be collected for 90 days after the end of treatment). Subjects who discontinue treatment for reasons other than first disease progression will have post-treatment follow-up for disease status until disease progression, initiating a non-study systemic chemotherapeutic treatment, withdrawing consent, becoming lost to follow-up, death, or 36 months post study registration whichever occurs first. Following first disease progression, subjects will be followed by telephone contact for overall survival until death, withdrawal of consent or 36 months post study registration, whichever comes first. The study will be stopped if greater than 30% of patients discontinue pembrolizumab due to an adverse event or for any patient death related to toxicity.

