- **Stable Disease (SD):** Failure to meet criteria for CR or PR, in absence of PD.

---

CONFIDENTIAL

*This document is confidential. Do not disclose or use unless authorized.*

- **Progressive Disease (PD):** At least 25% increase in the summed score for laryngeal and tracheo-bronchial involvement, confirmation by a repeat, consecutive assessment no less than 4 weeks from the date first documented.

Immunotherapeutic agents such as pembrolizumab may produce antitumor effects by potentiating endogenous tumor-specific immune responses which may be functionally anergic. The response patterns seen with such an approach may extend beyond the typical time course of responses seen with cytotoxic agents, and can manifest a clinical response after an initial increase in tumor burden or even the appearance of new lesions.

For those patients with pulmonary lesions measurable by RECIST 1.1, CT scans of the chest will be obtained every 12 weeks (84 days +/- 7 days) to assess response per RECIST 1.1 criteria. Standard RECIST criteria may not provide a complete response assessment of immunotherapeutic agents such as pembrolizumab. Therefore, RECIST 1.1 will be used with the following adaptation:

If radiologic imaging shows PD, tumor assessment should be repeated a minimum of 4 weeks later in order to confirm PD with the option of continuing treatment per below while awaiting radiologic confirmation of progression. If repeat imaging shows a reduction in the tumor burden compared to the initial scan demonstrating PD, treatment may be continued as per treatment calendar. If repeat imaging confirms progressive disease, subjects will be discontinued from study therapy. In determining whether or not the tumor burden has increased or decreased, all target lesions as well as non-target lesions should be considered.

In subjects who have initial evidence of radiological PD, it is at the discretion of the treating physician whether to continue a subject on study treatment until repeat imaging is obtained a minimum of 4 weeks later. This decision should be based on the clinical judgment of the subject's overall clinical condition, including performance status, clinical symptoms, and laboratory data. Subjects may receive treatment while waiting for confirmation of PD if they are clinically stable as defined by the following criteria:

- \*absence of signs and symptoms indicating disease progression
- \*no decline in ECOG performance status

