Clinical imaging assessed by laryngoscopy and tracheoscopy will be performed every 3 weeks (21 days $\pm$  3 days). In addition, a comprehensive laryngoscopy, tracheoscopy, and bronchoscopy will be performed every 4 cycles in the operating room.

VHI-10 questionnaire is required only for subjects enrolled after IRB approval and/or activation of Protocol AM 10

After 1 year, the clinical assessment will be reduced to 24 weeks for 12 months only.

*CONFIDENTIAL*

*This document is confidential. Do not disclose or use unless authorized.*

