### **10.1.2.6 Tumor Imaging and Assessment of Disease**

Clinical response rates will be the primary measure for assessment of tumor response and as a basis for all protocol guidelines related to disease status (e.g. discontinuation of study therapy). Clinical response will be assessed by direct visualization and scoring of disease burden within the upper aerodigestive tract (**Appendix A: Surgical Scoring and Appendix G: CRFs**).

The burden of disease will be assessed at each direct laryngoscopy/tracheoscopy examination performed in clinic and in the operating room, and the extent of papilloma growth will be measured using an instrument previously described [8, 9]. Briefly, evaluations will be made of five major anatomic sites in the larynx (epiglottis, false cords, ventricle, true cords, and subglottis), which are subdivided into 23 subsites. Four major anatomic sites in the tracheobronchial tree (trachea, tracheostomy site, if present, carina and mainstem bronchus) are divided into 6 subsites. The rating incorporates three components. Number of sites (AS) is the actual number of affected sites. For laryngeal disease, this value can range from 0 to 23. Surface area (SA) involvement at each major site is rated on the following scale: 0 (none), 1 (under 1/3 of area is affected), 2 (under 2/3 of area), or 3 (more than 2/3 of area). For the total of five major sites this value can range from 0 to 15. Extent of lumen obstruction (LO) reflects the degree of airway obstruction at each site, on a similar scale of 0-3. For the total of five major sites this

---

*CONFIDENTIAL*

*This document is confidential. Do not disclose or use unless authorized.*

value can range from 0 to 15. The three components (AS, SA and LO) are summed to yield a single overall rating, but the scores are entered separately into the computer to permit analysis of separate components of the score if desired. The potential range of this scoring system is 0 to 53 for laryngeal disease; the range observed in previous studies was 0 to 43 ([www.clinicaltrials.gov](http://www.clinicaltrials.gov); NCT00571701). Scores for tracheobronchial disease are calculated similarly. The maximum possible AS score is 6. The maximum SA and LO scores are each 12. Therefore, the maximum summed score for tracheo-bronchial involvement is 30. Copies of the scoring sheet pages are included in the appendix, as part of the case report forms (**Appendix A: Surgical Scoring and Appendix G: CRFs**).

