#### **10.1.2.6.1 Assessment of Response**

Overall response rates according to clinical assessment will be derived from time-point response assessments as follows:

- **Complete Response (CR):** Complete disappearance of all tumor lesions (and no new lesions). CR must be confirmed by repeated, consecutive assessments made no less than 4 weeks from the date first documented.
- **Partial Response (PR):** Decrease in the summed score for laryngeal and tracheo-bronchial involvement by 25% or greater by a consecutive assessment at least 4 weeks after first documentation.
- **Stable Disease (SD):** Failure to meet criteria for CR or PR, in absence of PD.
- **Progressive Disease (PD):** At least 25% increase in the summed score for laryngeal and tracheo-bronchial involvement, confirmation by a repeat, consecutive assessment no less than 4 weeks from the date first documented.

3-Dimension tracheal reconstruction with volumetric analysis and RECIST 1.1 will be applied as another measure for assessing tumor response in those patients with tracheal and/or pulmonary involvement, respectively, and will contribute to the basis for all protocol guidelines related to disease status (e.g. discontinuation of study therapy).

For those patients with pulmonary lesions measurable by RECIST 1.1, CT scans of the chest will be obtained every 12 weeks (84 days +/- 7 days) to assess response per RECIST 1.1 criteria. Imaging assessments will be adapted as follows to account for the unique tumor response seen in this class of therapeutics.

At the baseline imaging study, if there is no evidence of pulmonary disease measurable by RECIST 1.1, the patient will be followed with serial laryngoscopy/tracheoscopy examinations every 3 weeks and serial CT scans will be obtained every 6 months until the end of the study. If there is evidence of pulmonary disease, lymphadenopathy, and/or extra-tracheal disease (except those involving the larynx) measurable by RECIST 1.1, the patient will undergo repeat imaging every 12 weeks ( $\pm$  7 days). If two consecutive imaging assessments demonstrate SD or CR, the patient will undergo repeat imaging every 6 months until the end of the study. If imaging shows PD, tumor assessment should be repeated no less than 4 weeks from the date first documented in order to confirm PD with the option of continuing treatment for clinically stable subjects as discussed below in the Table.

Clinically stable is defined by the following criteria:

---

*CONFIDENTIAL*

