
*This document is confidential. Do not disclose or use unless authorized.*

\*Absence of signs and symptoms indicating disease progression

\* No decline in ECOG performance status

\*Absence of rapid progression of disease

	Clinical Stable		Clinically Unstable	
	Imaging	Treatment	Imaging	Treatment
1 st radiologic evidence of PD	Repeat imaging at $\geq$ 4 weeks to confirm PD	May continue study treatment at the Investigator's discretion while awaiting confirmatory can	Repeat imaging at $>4$ weeks to confirm PD if possible	Discontinue treatment
Repeat scan confirms PD	No additional imaging required	Discontinue treatment	No additional imaging required	N/A
Repeat scan shows SD, PR or CR	Continue imaging assessments	Continue study treatment at the Investigator's discretion	Continue imaging assessments if possible	May restart study treatment if condition has improved and/or clinically stable per Investigator's discretion

In determining whether or not the tumor burden has increased or decreased, all target lesions as well as non-target lesions should be considered. Subjects that are deemed clinically unstable are not required to have repeat imaging for confirmation. If radiologic progression is confirmed, then the subject will be discontinued from trial treatment. If radiologic progression is not confirmed, then the subject should resume/continue trial treatment and have their next scan in 12 weeks (84  $\pm$  7 days).

After the first documentation of progression, it is at the discretion of the investigator to keep a clinically stable subject on trial treatment or to stop trial treatment until repeat imaging performed at least 28 days later confirms progression. When feasible, subjects should not be discontinued until progression is confirmed. Subjects that are deemed clinically unstable are not required to have repeat imaging for confirmation. If progression is confirmed, then the subject will be discontinued from trial treatment. If progression is not confirmed, then the subject should resume/continue trial treatment.

---

*CONFIDENTIAL*

*This document is confidential. Do not disclose or use unless authorized.*

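### Section 7.1.2 lets a 3-week exam of a target lesion confirm endoscopic progression, but the protocol defines clinical progression as a summed-score rise confirmed at 4 weeks or later; the 7.7 removal list omits clinical progression

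*Combined protocol and SAP*

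**What the plan says.** **The dosing rule.** Section 7.1.2 gives drug after the operative endoscopy. If that endoscopy shows progression, drug continues "until the next in-office clinical examination in 3 weeks which confirms progressive disease of the target lesion".

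**The definition.** Section 4.2.3.1 defines clinical progression as "At least 25% increase in the summed score for laryngeal and tracheo-bronchial involvement". Section 10.1.2.6.1 repeats the definition and, like 4.2.3.1, requires "confirmation by a repeat, consecutive assessment no less than 4 weeks from the date first documented". The score adds the number of affected sites, surface area and lumen obstruction. It selects no target lesion; elsewhere the protocol uses that term only in its imaging text.

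**The role of clinical assessment.** Section 10.1.2.6 makes clinical response the primary measure and uses it "as a basis for all protocol guidelines related to disease status (e.g. discontinuation of study therapy").

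**The stopping text.** The synopsis (1.0) says "Treatment with pembrolizumab will continue until documented confirmed disease progression". Section 2.1 says "Treatment with pembrolizumab will continue until documented disease progression", without the word confirmed. The only progression item in the 7.7 list is confirmed radiographic progression. The same list has a general item for investigator decision.

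**The schedule.** Flow chart 9.1, note 22: "Clinical imaging assessed by laryngoscopy and tracheoscopy will be performed every 3 weeks", with a ±3-day window.

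**The concern.** Section 7.1.2 and the definition differ in two ways: when confirmation may happen (3 weeks against at least 4) and what is measured (a target lesion against a summed score). A site that follows 7.1.2 as written can record progression as confirmed at the 3-week visit.

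Two things follow from that label. The patient comes off drug, although 4.2.3.1 expects that some responses will appear after an initial increase. The patient also moves to survival follow-up under 10.1.5.4.1, which is a telephone contact every 24 weeks. A patient who stops without progression is instead examined every 8 weeks under 10.1.5.4. In a multi-site trial of about 22 adults, sites could handle the same finding differently.

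The 7.7 list raises a separate point. Patients with laryngeal disease only are eligible (5.1.2), and patients without RECIST-measurable lung disease are followed by 3-weekly endoscopy, with CT every 6 months (10.1.2.6.1). For these patients endoscopy is the main way to detect progression, yet the list does not name it.

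**Working it through.** **Inputs**
- Minimum confirmation interval: 4 weeks = 28 days (4.2.3.1, 10.1.2.6.1).
- Endoscopy interval: 21 days, window ±3 (2.1; flow chart note 22).
- Travel over 50 miles: ±7 days at each visit (flow chart note 1).
- Operating-room exams: every 84 days, ±7 in 10.1.2.7 and ±14 in 2.1.
- Endoscopy may fall within 24 hours either side of a dose (10.1.2.3), and the dose has its own ±3-day window (7.1.2).

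**Gap between first documentation and a later exam**

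Gap = nominal ± (window of index exam + window of later exam).

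| Situation | Next exam (days) | Second following exam (days) |
|---|---|---|
| Nominal | 21 | 42 |
| Only the later exam moves, ±3 | 21 ± 3 = 18–24 | 42 ± 3 = 39–45 |
| Both move, ±3 | 21 ± 6 = 15–27 | 42 ± 6 = 36–48 |
| Dose ±3 plus 24 hours, both exams | 21 ± 8 = 13–29 | 42 ± 8 = 34–50 |
| Operating-room index ±7, next ±3 | 21 ± 10 = 11–31 | 42 ± 10 = 32–52 |
| Travel, both ±7 | 21 ± 14 = 7–35 | 42 ± 14 = 28–56 |

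Under the ordinary ±3-day window the next exam is always short of 28 days. It reaches 28 only when a wider window, or the 24-hour allowance added to the dose window, is used near its limit. In every row, the second following exam is at 28 days or later.

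The ±14-day operating-room window would widen these ranges further: 21 ± 17 = 4–38 and 42 ± 17 = 25–59. I do not rely on them. Section 7.1.2 ties the operative exam to a dose with a ±3-day window, so an operative exam 4 days before the next cycle's exam does not fit the scheme. Stating the rule in days avoids having to settle this.

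**Doses after first progression.** Under a literal 7.1.2: day 0 only, stopping at day 21, so 1 dose. Under the 28-day definition on the nominal schedule: days 0 and 21, stopping at day 42, so 2 doses. The difference is 1 dose.

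**The 7.7 list.** Section 10.1.2.6 bases discontinuation on clinical response, while the list names radiographic progression only. The synopsis and 2.1 refer to disease progression without limiting it to imaging, and the list allows removal by investigator decision.

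**Simon design, as a background check.** With at most 1 response in 11 stopping the trial, the early-stopping probability at 15% is 0.85^11 + 11 × 0.15 × 0.85^10 = 0.167 + 0.325 = 0.492. Requiring at least 6 of 21 gives an exact probability of a positive conclusion of 0.079 at 15% and 0.857 at 38%. These reproduce the plan's 49%, 8% and 86%. They depend on counts of best response CR or PR; the progression-confirmation interval is not an input.

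**The case against.** The best defence is that 7.1.2 is only a dosing instruction. On this reading it tells sites not to withhold drug at first endoscopic progression, and if the next exam does not confirm it, dosing goes on. Section 10.1.2.6.1 supports this: "If progression is not confirmed, then the subject should resume/continue trial treatment". That section also lets the investigator either keep a clinically stable patient on drug or stop while awaiting confirmation at least 28 days later. Its text speaks of repeat imaging. The flow chart labels endoscopy as clinical imaging, so applying it to endoscopy is plausible but not certain. Some variation between sites is therefore built into the plan, and stopping early is not in itself a breach. This reduces the harm. It does not repair the sentence, which still says that the 3-week exam confirms progression and still names a measure the score does not contain.

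A second objection is that the tension lies partly in the definition. It asks for a consecutive assessment at least 4 weeks later when exams are 3 weeks apart. That is fair, and shortening the interval to 3 weeks is an available alternative. It would, however, change an endpoint definition in two sections, and CR and PR carry the same 4-week minimum. Editing 7.1.2 is the smaller change. What consecutive means when an exam falls in between remains for the sponsor to settle.

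A reader might also infer that patients with clinical progression have no route off treatment. The synopsis, 2.1 and the investigator-decision item show otherwise.

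**Conclusion.** The inconsistency is real and minor. Section 7.1.2 attaches confirmation to an exam at a nominal 21 days (15–27 with both visits at ±3) and to a target lesion. The definition requires 28 days and a summed score. The consequence is a possible premature label of confirmed progression, with drug stopped about one dose earlier and a move to telephone follow-up. Section 7.7 has a list inconsistency.

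This rests on two assumptions: visits run on the 3-weekly schedule, and sites take the last sentence of 7.1.2 at its word.

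Two stronger conclusions might be drawn, and the documents support neither. The first is that the 3-week exam can never qualify; under the wider windows it can. The second is that the primary analysis is compromised. The Simon operating characteristics are unaffected. The flow chart still marks endoscopy after discontinuation, so progression could be confirmed off drug. Any effect on response rate or response duration is indirect and cannot be quantified from the documents.

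**What to change.** - **7.1.2:** replace the last sentence with wording such as: *the patient may continue pembrolizumab, at the investigator's discretion as in 10.1.2.6.1, until progressive disease by summed score is confirmed at the first scheduled examination at least 28 days after first documentation (normally the second following 3-weekly visit).* The reference to a target lesion is deleted.
- **7.7:** add *confirmed clinical (endoscopic) progression per 10.1.2.6.1* to the list.

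The cost is amendment wording in two sections and about one extra dose for a true progressor who stays on drug. No visits are added, because the 3-weekly exams are already scheduled. Keeping the wording permissive preserves the investigator's existing discretion to stop before confirmation.
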